18.0 Annual reporting

Development Annual Safety Update (DSUR)

The DSUR will be written by the CI (using the Sponsor's template) and submitted to the sponsor for review prior to submission to the MHRA. The DSUR is due for submission within 60 days of the end of the reporting period. The reporting period is annually from the date on the "notice of acceptance letter" from the MHRA. As delegated Sponsor Medical Assessor the CI will carry out a risk benefit analysis of the IMPs encompassing all events having arisen on the trial. REC will be sent a copy of the DSUR. Any findings in the DSUR that are inconsistent with the Investigator Brochure should be communicated to AZ during DSUR production but at the latest in parallel to the DSUR being sent to the RA/Ethics committee.

Annual Progress Report (APR)

The APR will be written by the CI (using HRA template) and submitted to the sponsor for review prior to submission to the REC. The APR is due within 30 days of the anniversary date of the "favourable opinion" letter from the REC.

19.0 Statistical and Data Analysis

19.1 Sample size calculation

n=25 in each arm. This is a pilot/exploratory study: the numbers were chosen as this was felt to be feasible given the resources of the site, and will enable generation of data for a larger scale trial should the results of this pilot be encouraging.

19.2 Planned recruitment rate

Based on analysis from the renal unit at the Royal London Hospital (where the study will be based), around 140 transplants are performed per year, of which 30% have type 2 diabetes. We expect up to 20% of patients to decline to take part. Therefore, it is expected that the recruitment will be complete within 16-20 months.

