5.0 Trial Summary

Full title	AZD1656 in Transplantation with Diabetes tO PromoTe Immune TOleraNce
Short title and/or Acronym	The ADOPTION Study
Trial Design	Single site, placebo controlled, double blind randomised
Methodology	clinical trial.
Phase of the Trial	11
Study Duration	27 months
Study setting	Single NHS site
Investigational Medicinal Product(s)	AZD1656
Medical condition or disease under investigation	Post-renal transplant diabetes and graft rejection
Planned Sample Size	50
(Maximum) Treatment duration	3 months
Follow up duration	9 months
End of Trial definition	The last patient has completed their last follow up point at 1 year post-transplant (data review visit).

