11.4 Exploratory or Tertiary Endpoints/outcomes

- 1) 12-month graft function (eGFR) and diabetic control (HbA1c; medication review) to assess legacy effect (potential follow up publication)
- 2) Differences in other peripheral T cell populations, measured by FACS analysis
- 3) Histological staining for Treg cells in any renal biopsy taken for clinical indications between baseline and month 3 protocol biopsy
- 4) Differences in the functional phenotype of the Treg cells

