13.7.3 Follow-up Procedures

After the last patient has completed visit 7, there will be an interim deadlock, at which point we will analyse the primary endpoint data.

At 1 year post-transplant the patient's medical records will be reviewed for the following data which will be extracted: Graft function as measured by eGFR and serum creatinine Episodes of rejection Episodes of infection Diabetic control measured by HbA1c

Current anti-diabetic medication regimen

We will then perform a secondary data analysis.

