13.10 End of trial (EOT)

It is the CI's responsibility to submit the EOT notification to REC and MHRA once obtaining sponsor approval. The EOT notification must be received by REC and MHRA within 90 days of the end of the trial.

If the study is ended prematurely, the Chief Investigator will notify the Sponsor, REC & MHRA including the reasons for the premature termination (within 15 days).

End of Trial definition: is after the last patient has completed their last follow up point at 1 year post-transplant (data review visit).

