19.3 Statistical analysis plan (SAP)

Please refer to SAP for full details

Primary Endpoint

The primary endpoint is the change in mean peripheral Treg cell number between baseline and 3 months measured using FACS analysis between AZD1656 and placebo.

This will be analysed at the first data analysis.

Secondary Endpoints:

- 1) Histological staining for Treg cells in renal biopsy tissue between baseline and 3 month protocol biopsy
- Incidence of delayed graft function, defined as the need for dialysis within 1 week post-transplant
- 3) Diabetic control between baseline and month 3 using change in HbA1c measurement
- 4) Dose of other anti-diabetic medication between baseline and month 3 (descriptive)
- 5) Safety endpoints i.e. number of hypoglycaemic episodes (descriptive)
- 6) Insulin resistance: HOMA IR measurement at month 3
- 7) Graft function: (eGFR) at month 3
- 8) Episodes of acute rejection (defined as biopsy proven acute rejection)
- 9) Episodes of opportunistic infections: bacterial and viral (descriptive)

All of these endpoints will be analysed at the first data analysis; endpoints 8 and 9 will also be re-examined at the second data analysis.

Exploratory or Tertiary Endpoints/outcomes

- 1) 12-month graft function (eGFR) and diabetic control (HbA1c; medication review) to assess legacy effect (potential follow up publication)
- 2) Differences in other peripheral T cell populations, measured by FACS analysis
- 3) Histological staining for Treg cells in any renal biopsy taken for clinical indications between baseline and month 3 protocol biopsy
- 4) Differences in the functional phenotype of the Treg cells

Endpoints 2 and 3-4 will be analysed at the first data analysis; endpoint 1 will be analysed at the second data analysis.

Baseline Demographics and Biochemical parameters

Demographics and Clinical Characteristics

- Age at recruitment (derived from date of birth; continuous)
- Sex (categorical)
- Self-reported ethnicity (using ONS categories; categorical)
- Weight (continuous)
- Systolic BP (continuous)
- Diastolic BP (continuous)

Medical History

- Cause of end stage renal failure (categorical)
- Dialysis modality (categorical)
- Dialysis vintage (continuous)
- Diabetes duration (continuous)
- Retinopathy (yes/no, categorical)
- Neuropathy (yes/no, categorical)
- Coronary artery disease (yes/no, categorical)
- Peripheral artery disease (yes/no, categorical)
- Cerebrovascular disease (yes/no, categorical)

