19.7 Interim analysis and criteria for the premature termination of the trial

There will be an interim datalock after the last patient has completed visit 7, at which point we will analyse the primary endpoint data and the relevant secondary and tertiary endpoints. There will be a secondary analysis after the final data collection review one year after transplant.

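### Is the stated 27-month study duration too short for the protocol's own recruitment forecast plus one year of follow-up, and does that call for a change?

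*Combined protocol and SAP*

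**What the plan says.** The summary table in protocol section 5.0 lists a study duration of 27 months, 50 patients, 3 months of treatment and 9 months of follow-up. The same table ends the trial at the last patient's one-year data review. Section 13.10 repeats this, placing the end "after the last patient has completed their last follow up point at 1 year post-transplant".

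Section 19.2 gives the accrual inputs: around 140 transplants a year, of which 30% are in patients with type 2 diabetes. On refusals it says "We expect up to 20% of patients to decline to take part", and it concludes that "it is expected that the recruitment will be complete within 16-20 months".

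Section 12.1 requires transplantation within the previous 24 hours, so one year post-transplant is in effect one year after entry. The schedule in section 13.7.1 allows two weeks either side of the one-year review.

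There are two analyses. The first follows the datalock after the last patient's visit 7 (sections 13.7.3 and 19.7). For the later one, section 19.7 says "There will be a secondary analysis after the final data collection review one year after transplant". It covers the exploratory endpoint "12-month graft function (eGFR) and diabetic control (HbA1c; medication review) to assess legacy effect" (section 11.4). Section 19.3 adds, for acute rejection and opportunistic infection, that "endpoints 8 and 9 will also be re-examined at the second data analysis".

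**The concern.** The length of a trial that ends at the last patient's final review is the recruitment period plus one patient's follow-up. On the protocol's own forecast even the quickest case, 16 + 12 months, exceeds the stated 27. No section reconciles the two figures.

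If 27 months were a real limit, the part of the trial beyond it would be the last patients' one-year records review. That review supplies 12-month eGFR and HbA1c, and the second look at rejection and infection. A reader could fear either that recruitment would be cut short to fit or that these late data would be incomplete.

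**Working it through.** **Inputs.** 50 patients, 27 months, and 3 + 9 = 12 months per patient (section 5.0). 140 transplants a year, 30% with type 2 diabetes, at most 20% declining, and recruitment in 16 to 20 months (section 19.2). Entry within 24 hours of transplant (section 12.1). Review window of plus or minus 2 weeks, and visit 7 at 12 + 2 weeks (section 13.7.1).

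**1. Reproduce the recruitment forecast.** Candidates per year: 140 x 0.30 = 42. With 20% declining: 42 x 0.80 = 33.6 a year, or 2.8 a month. Recruitment: 50 / 2.8 = 17.9 months, which lies inside 16 to 20. The forecast follows from its inputs.

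**2. Total duration.** Duration = recruitment + 12 months.

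| Case | Recruitment (months) | Total (months) | Excess over 27 |
|---|---|---|---|
| Lower end of forecast | 16 | 28 | 1 |
| 20% decline | 17.9 | 29.9 | 2.9 |
| Upper end of forecast | 20 | 32 | 5 |

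Two weeks is 14 / 30.44 = 0.46 months. With the review window the range is 28 - 0.46 = 27.5 to 32 + 0.46 = 32.5 months, so the excess is about 0.5 to 5.5 months.

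**3. What 27 months would need.** Recruitment in 27 - 12 = 15 months, that is 50 / 15 x 12 = 40 patients a year. Participation: 40 / 42 = 95.2%, so 4.8% declining. With nobody declining, recruitment takes 50 / 42 x 12 = 14.3 months and the trial 26.3. The 20% is a ceiling, so a decline of 0 to 4.8% satisfies the wording of section 19.2 and allows 27 months. It does not agree with that section's conclusion: 16 months corresponds to 50 / 16 x 12 = 37.5 a year, or 37.5 / 42 = 89.3% participation, and 20 months to 30 a year, or 71.4%. The 29.9 months is therefore the 20%-decline case and not a rate that the protocol states.

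**4. What depends on the figure.**

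- *First datalock.* It needs the last visit 7, 14 weeks (3.2 months) after the last entry: month 16 + 3.2 = 19.2 to 20 + 3.2 = 23.2. With both one-week visit windows used in full it is 16 weeks (3.7 months), at latest month 23.7. The primary endpoint and the 3-month endpoints are complete before month 27.
- *Second analysis and end of trial.* Both are tied to the last one-year review and to no calendar date.
- *One-year review.* Section 13.7.3 makes this a records extraction, in which "medical records will be reviewed for the following data which will be extracted". It needs no study treatment and no research visit.
- *Sample size.* Section 19.1 sets 25 per arm on feasibility and does not refer to the duration.

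**The case for a change.** The strongest case for a correction is that the summary table is what many readers look at first, and its duration cannot be met on the protocol's own forecast. The usual explanations do not remove the gap. The review window still leaves 27.5 months at best, and counting set-up or reporting time would widen it. Very low refusal would close it only by recruiting faster than the 16-month lower end of the forecast. Exclusions, and patients unable to decide within 24 hours, would if anything slow recruitment. The correction would also be cheap, at one table entry.

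The case can be pressed further by supposing that someone enforces 27 months. Patients entered after month 15 would then lack the one-year review. In the 20%-decline case 15 x 2.8 = 42 would have entered by then, leaving 8 of 50. At the two ends of the forecast it would be about 3 (50 - 15 x 50/16 = 3.1) and about 13 (50 - 15 x 50/20 = 12.5).

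The inconsistency itself stands. The patient counts do not, because they need a cut-off that appears nowhere in the documents and that would contradict the end-of-trial definition in sections 5.0 and 13.10. Nor do the documents show which figure is the slip: 15 + 12 = 27 could reflect a different recruitment assumption. That weakens any claim that one particular replacement is right.

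**Conclusion.** The arithmetic is correct: 28 to 32 months on the forecast against 27 stated, an excess of 1 to 5 months, or about 0.5 to 5.5 with the review window. This assumes that the duration runs from first enrolment to the last one-year review. Section 5.0 gives no start point, and an earlier start would only enlarge the difference.

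No change to the plan follows. The 27 months is an isolated planning figure. The end of trial is defined by an event, the first datalock falls at about month 19 to 24, and the second analysis waits for the last review whenever that occurs. Anyone running the trial would follow the definition in section 13.10 and collect the last records. Correcting the entry would alter no design feature, visit, data item or analysis, and no endpoint or conclusion is at risk from leaving it. It is a clerical slip.

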19.3 Statistical analysis plan (SAP)

Please refer to SAP for full details

Primary Endpoint

The primary endpoint is the change in mean peripheral Treg cell number between baseline and 3 months measured using FACS analysis between AZD1656 and placebo.

This will be analysed at the first data analysis.

Secondary Endpoints:

- 1) Histological staining for Treg cells in renal biopsy tissue between baseline and 3 month protocol biopsy
- Incidence of delayed graft function, defined as the need for dialysis within 1 week post-transplant
- 3) Diabetic control between baseline and month 3 using change in HbA1c measurement
- 4) Dose of other anti-diabetic medication between baseline and month 3 (descriptive)
- 5) Safety endpoints i.e. number of hypoglycaemic episodes (descriptive)
- 6) Insulin resistance: HOMA IR measurement at month 3
- 7) Graft function: (eGFR) at month 3
- 8) Episodes of acute rejection (defined as biopsy proven acute rejection)
- 9) Episodes of opportunistic infections: bacterial and viral (descriptive)

All of these endpoints will be analysed at the first data analysis; endpoints 8 and 9 will also be re-examined at the second data analysis.

Exploratory or Tertiary Endpoints/outcomes

- 1) 12-month graft function (eGFR) and diabetic control (HbA1c; medication review) to assess legacy effect (potential follow up publication)
- 2) Differences in other peripheral T cell populations, measured by FACS analysis
- 3) Histological staining for Treg cells in any renal biopsy taken for clinical indications between baseline and month 3 protocol biopsy
- 4) Differences in the functional phenotype of the Treg cells

Endpoints 2 and 3-4 will be analysed at the first data analysis; endpoint 1 will be analysed at the second data analysis.

Baseline Demographics and Biochemical parameters

Demographics and Clinical Characteristics

- Age at recruitment (derived from date of birth; continuous)
- Sex (categorical)
- Self-reported ethnicity (using ONS categories; categorical)
- Weight (continuous)
- Systolic BP (continuous)
- Diastolic BP (continuous)

Medical History

- Cause of end stage renal failure (categorical)
- Dialysis modality (categorical)
- Dialysis vintage (continuous)
- Diabetes duration (continuous)
- Retinopathy (yes/no, categorical)
- Neuropathy (yes/no, categorical)
- Coronary artery disease (yes/no, categorical)
- Peripheral artery disease (yes/no, categorical)
- Cerebrovascular disease (yes/no, categorical)
- Hypertension (yes/no, categorical)
- Heart failure (yes/no, categorical)

Pregnancy test

• Pregnancy test negative (either serum or urine) (yes/no, categorical)

Transplant details

- Cold ischaemia time in hours (continuous)
- Warm ischaemic rime minutes (continuous)
- Donor age (continuous)
- ECD (yes/no, categorical)
- CMV mismatch (yes/no, categorical)
- HLA mismatch (categorical)

Medication

Each medication will be recorded as name/dose/start date (categorical)

Biochemical Parameters

- Fasting c-peptide (continuous)
- Fasting cholesterol (continuous)
- Haemoglobin (continuous)
- Serum sodium (continuous)
- Serum potassium (continuous)
- Serum urea (continuous)
- Serum creatinine (continuous)
- eGFR (CKD-EPI formula, continuous)
- Serum albumin (continuous)
- Serum alkaline phosphatase (continuous)
- Serum bilirubin (continuous)
- Serum alanine aminotransferase (continuous)
- Serum calcium (continuous)
- Serum phosphate (continuous)
- C-reactive protein (continuous)
- Glucose (continuous)
- Haemoglobin A1C (DCCT aligned; continuous)
- Peripheral Treg Cell number (interval)
- HOMA IR (continuous)

19.4 Summary of baseline data and flow of patients

The IMP versus placebo groups will be compared using standard statistical methods.

19.5 Primary outcome analysis

The endpoint data will be analysed on an ITT basis, with no subgroup analysis using unpaired parametric and non-parametric analysis as necessary, comparing the

change in mean Treg cell number between baseline and month 3 between the 2 groups.

Continuous variables will be tested for normality using D'Agostino-Pearson normality test. Mean (standard deviation), median (interquartile ranges) will be displayed along with max-min point estimate and confidence intervals. Statistical analysis will be by student t-test (unpaired) or Mann-Whitney U test.

Categorical data will be analysed by Chi Square test.

Statistical significance considered if P-value <0.05.

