11.3 Endpoints11.3.1 Primary Endpoint

The primary endpoint is the change in mean peripheral Treg cell number between baseline and 3 months measured using flow cytometry analysis (FACS) between AZD1656 and placebo.

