11.5 Objectives and Endpoints Summary

Objective	How objective measured	Outcome
Examine the effect of AZD1656 on Treg cell migration	Change in peripheral Treg population between randomisation and month 3 measured by mean change in Treg cell number between baseline and 3 months using FACS analysis.	Does AZD1656 lead to enhanced migration as demonstrated by a fall in peripheral Treg population over time compared to placebo?
Examine the effectiveness of AZD1656 on diabetic control	Change in HbA1c between baseline and month 3 visit, HOMA-IR at month 3, descriptive change in anti diabetic medication dose/need for additional anti-diabetic therapy.	Is there a difference between placebo and IMP on diabetic control/insulin resistance?
To investigate the effect of AZD1656 on renal transplant function	Renal function (eGFR CKD EPI) measured at 3 months and 12 months.	Is there a difference between AZD1656 and placebo treated patients' renal function at 3 and 12 months?
To determine the safety of AZD1656 to control diabetes post- transplant.	Patient and graft survival, number and type of AE (hypoglycaemic episodes, infective episodes), number and type of SAE, rejection rates (defined as incidence of biopsy proven acute rejection)	Is there a difference between placebo and AZD1656 treated groups in terms of number of AE, SAE, renal function and rejection rates?
Effect of AZD156 on Treg cell infiltration in renal transplant tissue	Change in Treg staining on renal biopsies collected as standard of care at implantation and 3 months post transplant.	Is there a difference between placebo and AZD1656 treated groups in terms of change in Treg cell infiltration between baseline and 3 month transplant biopsy?

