14.2 Sample Collection/Labelling/Logging

Samples will be collected by the research nurse or trained phlebotomist as per standard of care.

Samples will be labelled with patient identification and sent to the local labs as per routine care and the results logged on the pathology system and transcribed to the CRF.

The only samples that will be sent to the local lab, which are not part of routine care, are for serum C-peptide.

Volume of samples to be collected:

The total volume of blood which will be taken on top of routine care is:

1 table-spoon (approximately 20ml) of blood per clinic visit (4x 6ml samples of blood) in lithium heparin tubes provided locally.

In addition, 20ml of blood will be taken at visit 1, 2, 6 and 7 for Treg quantification via FACS. This sample will be taken to the Royal London Immunology laboratories by members of the study team for processing.

Any biopsy material will be processed and stored as part of routine clinical care.

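### The primary Treg analysis uses no baseline covariate and lets the data choose between t-test and Mann-Whitney; one pre-specified ANCOVA on data already collected would usually be more precise and, on a named scale, would fix the effect measure.

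*Combined protocol and SAP*

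**What the plan says.** Section 11.3.1 defines the endpoint: "The primary endpoint is the change in mean peripheral Treg cell number between baseline and 3 months", compared between arms. The summary table in section 11.5 has "mean change in Treg cell number between baseline and 3 months using FACS analysis".

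Section 19.5 plans an intention-to-treat comparison using "unpaired parametric and non-parametric analysis as necessary", and then states: "Statistical analysis will be by student t-test (unpaired) or Mann-Whitney U test". It names the D'Agostino-Pearson test for normality. It gives no cut-off, does not say whether the check is run per arm or pooled, and has no sentence linking its result to the test used. It promises a "max-min point estimate and confidence intervals" without naming the contrast they describe. No covariate or adjusted model appears.

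The baseline value is available. Section 14.2 says "20ml of blood will be taken at visit 1, 2, 6 and 7 for Treg quantification via FACS"; Visit 1 is randomisation and Visit 6 is week 12 (section 13.7.1). Section 19.3 lists peripheral Treg number among the baseline variables.

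Section 19.1 sets 25 per arm on feasibility, with no power calculation, and says the study "will enable generation of data for a larger scale trial should the results of this pilot be encouraging". Section 19.3 refers to a SAP for full details; no separate SAP text was among the documents supplied.

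**The concern.** There are two separate weaknesses.

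**Precision.** Analysing change uses the baseline only by subtraction, which forces its coefficient to 1. ANCOVA estimates that coefficient and is asymptotically never less precise. With 25 per arm, the planned comparison reaches 80% power (normal approximation) only for a difference of (1.960 + 0.842) × √(2/25) = 0.79 SD of change, so precision is scarce.

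**Effect measure.** The endpoint is a mean change, which a t-test addresses. A Mann-Whitney test compares rank ordering and does not estimate a difference in means. If the normality check selects the test, the data decide which kind of result is reported, and the promised intervals are not tied to either.

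Both matter because the main product of this pilot is an estimate and its interval. An interval wider than the data allow, on a scale not fixed beforehand, is less use for planning the next trial.

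**Working it through.** **Inputs from the documents:** 25 per arm (section 19.1); significance at P<0.05 (section 19.5, sidedness not stated, two-sided assumed). The sample size cannot be reproduced, because no effect size, SD or power is stated.

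**Assumed inputs, shown as ranges because the documents give none:** ρ, the baseline to month-3 correlation; k, the baseline SD divided by the month-3 SD; the effect size; and, for skewed data, the coefficient of variation (CV).

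**Step 1: variance.** With month-3 SD σ:
- variance of change = σ²(1 + k² − 2ρk)
- ANCOVA residual variance = σ²(1 − ρ²)
- ratio R = (1 − ρ²)/(1 + k² − 2ρk); interval width scales with √R; the equivalent change-score sample is 25/R per arm.

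Example, k=1 and ρ=0.5: R = 0.75/1.00 = 0.75, √R = 0.87, 25/0.75 = 33 per arm.

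| k | R at ρ = 0.3 / 0.5 / 0.7 | √R | Equivalent n per arm |
|---|---|---|---|
| 1 | 0.65 / 0.75 / 0.85 | 0.81 / 0.87 / 0.92 | 38 / 33 / 29 |
| 0.5 | 0.96 / 1.00 / 0.93 | 0.98 / 1.00 / 0.96 | 26 / 25 / 27 |
| 1.5 | 0.39 / 0.43 / 0.44 | 0.62 / 0.65 / 0.67 | 65 / 58 / 56 |

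**Step 2: small-sample cost.** Estimating the slope inflates the variance by about 1 + 1/(50 − 4) = 1.022, and the t quantile (47 v 48 df) by 1.0005. When R = 1, the interval is therefore √1.022 × 1.0005 = 1.01 times as wide. Median simulated width ratios at ρ = 0.3/0.5/0.7 agree: 0.82/0.88/0.94 (k=1), 1.00/1.01/0.98 (k=0.5) and 0.63/0.67/0.68 (k=1.5).

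**Step 3: power, normal data** (10,000 simulated trials per cell; true difference 0.7 month-3 SD). The written rule was taken as D'Agostino-Pearson on change in each arm, Mann-Whitney if either P<0.05, otherwise the t-test.

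| k | Written rule, ρ = 0.3 / 0.5 / 0.7 | ANCOVA |
|---|---|---|
| 1 | 53 / 69 / 87% | 71 / 79 / 92% |
| 0.5 | 70 / 80 / 90% | 71 / 79 / 92% |
| 1.5 | 35 / 45 / 62% | 71 / 79 / 92% |

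**Step 4: power, skewed data** (log-normal, 30% fall, equal log-scale SDs, ρ on the log scale).

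| Analysis | CV 0.5, ρ = 0.3 / 0.5 / 0.7 | CV 0.8 |
|---|---|---|
| Written rule | 48 / 61 / 81% | 24 / 32 / 46% |
| ANCOVA, raw counts | 73 / 79 / 91% | 35 / 41 / 53% |
| Log change, unadjusted | 59 / 74 / 92% | 31 / 42 / 61% |
| ANCOVA, log counts | 77 / 85 / 95% | 44 / 52 / 67% |

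Part of the log-ANCOVA gain comes from the scale; at ρ = 0.7 most of it does.

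**Step 5: validity and test choice.** Simulated type I error is 4.6–5.4% for the written rule, 4.2–5.2% for raw-count ANCOVA and 4.7–5.3% for log ANCOVA. Applied per arm, the normality check switches to Mann-Whitney in about 11% of trials with exactly normal data and in 48–80% of log-normal trials with no effect. In a further simulation (3,000 trials per scenario; normal, and log-normal with log-scale SD 0.6), per-arm and pooled checks chose differently in about 9–19% of trials. Running both tests and keeping the smaller P would give a type I error of about 5–7%.

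**The case against.** The strongest case is that nothing in section 19.5 is wrong. An unpaired comparison of change in a randomised trial is unbiased, its type I error is nominal, and no passage contradicts another. The trial is an exploratory pilot that makes no power claim. Naming D'Agostino-Pearson, and then one parametric and one non-parametric test, reads naturally as a rule, and the endpoint itself is described consistently as change in Treg number. The covariates and the exact rule are what a SAP would hold, and section 19.3 points to one. The gain rests on unseen inputs: R runs from 0.39 to 1.00 over the grid, and nothing says which cell applies. At CV 0.8, raw-count ANCOVA is matched or beaten by an unadjusted log change at ρ = 0.5 and 0.7, so the scale can matter as much as the covariate.

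Much of this stands. This is an improvement in efficiency and pre-specification, not the correction of an error, and it applies only to the supplied text. ANCOVA fixes the effect measure only if its scale is fixed too. But the normality rule is incompletely written, and the interval has no named contrast. The trade is also lopsided: about 1% wider at worst over this grid, more than a third narrower at best.

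**Conclusion.** The concern holds. In the supplied text the primary comparison has no baseline covariate, and the choice of test, and with it the reported effect measure, is left to an incompletely specified normality check. The planned test is valid.

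With equal SDs and ρ from 0.3 to 0.7, baseline adjustment narrows the interval by 8–19% asymptotically (6–18% simulated), equivalent to 29–38 patients per arm instead of 25. With a baseline SD half the month-3 SD the gain is close to nil; with a baseline SD 1.5 times as large, the interval is about a third narrower or better. These sizes depend on assumed ρ, k and skewness. The general advantage of ANCOVA and the availability of the baseline measurement do not. The change should be made, with medium confidence given the SAP that was not seen.

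**What to change.** First check whether the SAP cited in section 19.3 already specifies the model. If it does, bring section 19.5 into line with it. If not, before unblinding:

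- Drop the normality check as the selector of the test, and name one primary model in section 19.5: ANCOVA of month-3 Treg count on arm and baseline Treg count, reporting the adjusted between-arm difference with its 95% CI. Raw counts keep the stated difference in means.
- If a log scale is preferred, choose it in advance, report a ratio of geometric means, and align sections 11.3.1, 11.5, 19.3 and 19.5.
- Keep a rank test as a sensitivity analysis.
- Adjust change in HbA1c for its baseline in the same way. HOMA-IR is a month-3-only endpoint, so adjusting for its listed baseline is optional; the variance factor there is 1 − ρ² (0.91/0.75/0.51 at ρ = 0.3/0.5/0.7), not R.

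The cost is one degree of freedom, about 2% variance inflation at N=50, and a few sentences. No new data, visits or patients are needed.
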